- ii. **Exercise:** Sedentary lifestyle is associated with increased morbidity and mortality³³ and exercise training has been demonstrated to improve a number of important risk factors of medical burden (i.e., weight, cholesterol, insulin level^{34, 35}). Exercise may be dually beneficial for BD given that it has also been found to improve mood^{36, 37}. In a unipolar depressed sample, exercising 3 days/week for 45-min was as effective in reducing depressive symptoms as an antidepressant (i.e., sertraline)^{38, 39}, with promising data for bipolar samples⁴⁰. Given the duality of exercise benefit for mental health, interventions are needed to increase lifestyle activity.
- iii. **Wellness:** Individuals with BD make poor food choices³¹ and use maladaptive coping strategies for stress, such as smoking, that increase their medical burden. For example, smoking in BD populations has been shown to increase heart disease mortality⁴¹. Individuals with BD have dysregulated behavioral activation systems⁴² which may explain why they chose rewarding activities (i.e., cigarettes, caffeine), opposed to healthier coping skills. It is essential that an intervention reinforce the importance of making healthy lifestyle choices (i.e., food choices, lifestyle activity, reducing caffeine).

II. SPECIFIC AIMS

The purpose of this research is to develop and test the feasibility and acceptance of a theoretically integrated treatment to address the impact of medical comorbidity of individuals with BD, while exploring its efficacy, whether it improves overall functioning and symptoms, as well as examine a potential moderator and mediator of treatment response. NEW Tx is a proposed solution to this problem as it builds upon previous empirical studies in healthy populations as well as the limited literature on lifestyle modification with serious mental illness. NEW Tx also integrates and modifies treatment strategies, such that it can be administered by a sole provider who is skilled in intervention and assessment of medical comorbidity and BD. NEW Tx is not intended to replace the need to collaborate with other providers, and strongly encourages such support as needed, but is a first-line, adjunct treatment to reduce the medical burden in individuals with BD.

A. Primary Aims

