NEW Tx is a flexible modular treatment such that modules are selected based on the needs of the individual to increase its generalizability across patients, settings, and providers as well as its acceptability to patients. The three modules of the intervention are as follows:

A. Nutrition/Weight Loss Module

To enhance nutrition, we review nutritious foods (e.g., high in vitamins and minerals, low in fat) in each of the food groups as well as teach participants how to calculate serving size to enhance portion control. We discuss the importance of a “balanced diet” as well as having essential vitamins and minerals, particularly ones that may be beneficial for mood disorders. Finally, we review food that may be unhealthy and why. Weight loss is tracked as needed and food diaries are used as needed (at minimum at baseline, week 10, and week 20) to monitor participants’ daily foods consumed and calories. Participants, with guide from their NEW Tx therapist, will determine a daily goal for caloric intake to assist in identifying healthy and realistic weekly weight loss goal. We utilize Cognitive Behavioral Therapy (CBT) strategies to challenge negative thoughts about changing food choices⁴⁴. We also include a session on emotional eating, or eating to cope with negative affect, by evaluating the accuracy of thoughts associated with the craving. We discuss positive coping strategies, or distraction activities, to replace food as a way to improve mood or “comfort” oneself. We also utilize the philosophy from Brownell’s LEARN program⁴⁵ that there are no “forbidden foods” as evidence suggests that this may increase cravings for these foods as well as negative thoughts about the module⁴⁶. We use psychoeducational materials to enhance adherence. We specifically discuss the impact of “psychological factors” and review research studies of diet programs that have had positive outcomes in severe mental illness. Finally, we employ behavioral strategies in NEW Tx, such as positive reinforcement, to enhance adherence through the use of reward charts. We then collaboratively set homework and weekly goals each session.

B. Exercise Module

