The goal of this module is to exercise 5 days/week, for at least 30 min each day, of moderate intensity⁴⁷. Participants complete the Exercise Questionnaire each session to track their exercise. We begin this module by discussing the importance and rationale for exercise. We review evidence that exercise is particularly important in enhancing mood. We also discuss ways of increasing *lifestyle activity* (i.e., taking the stairs, standing instead of sitting, walking to the store). In this way, we approach exercise as a task not requiring sustained or extreme energy, concentration, and motivation, but a more casual experience, which can last for a relatively short period of time and still be helpful. This paradigm shift in conceptualizing exercise as lifestyle activity is very important for individuals who have a vulnerability to think negatively about themselves, their world, and their future. We utilize CBT strategies to challenge negative thoughts about exercising, which for individuals with BD is often their most significant obstacle^{44, 48}. We also set weekly exercise goals and discuss participants’ obstacles to adhering to these goals. Many exercise programs encourage participants to find a “work out partner”⁴⁵. This can be especially problematic for individuals with BD who tend to isolate when depressed or have interpersonal problems when manic⁴⁸. Given that social support is still a very important motivator and can buffer against future episodes^{49, 50}, we discuss the concept of “structured, group lifestyle activities.” Feedback from our pilot groups suggests that this is immensely helpful, even participants with anxiety report that they can tolerate *structured* groups as they do not feel pressure “to perform” or “to interact with others.” Some participants from our pilot group have noted that exercising when manic helps them to stay focused and keep their energy level down, while others have reported the opposite effect. Similarly, some participants reported choosing to exercise in the evening as it helps them to relax and sleep, while others report needing “wind down time” after exercising. By including individuals with manic symptoms, we will learn more about the association of exercise and mania.

C. Wellness Module

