- ii. **Phase II:** In this phase, we will pilot test the NEW Tx methods compared to TAU ($n = 60$) to further examine feasibility, to estimate an effect size, and to explore its efficacy for reducing medical burden. TAU will be the control group in the Phase II pilot study as it is the standard treatment in the Massachusetts General Hospital (MGH) Bipolar Clinic and Research Program. Participants randomized to TAU who complete the first 20 weeks of the study will have the option to receive NEW Tx. TAU participants who chose to receive NEW Tx (the waitlist group) will follow the same procedures as the NEW Tx group over an additional 20 weeks such that they will have assessments at Weeks 30, (mid-treatment), 40 (post-treatment), and 52 (follow-up) (see Table 2). For TAU, medication and dosage changes are allowed as long as the change is recommended based on the guidelines and participants remain on a mood stabilizer. Medication changes will be monitored with the Clinical Monitoring Form Medication Module. All participants will have a three-month follow-up visit during which post-treatment measures and assessments will be repeated. Participants will be recruited with the same criteria as the nonrandomized trial, but will be randomized using a 1:1 allocation ratio with a blocking strategy. The assessments will be similar to those used in Phase I. In addition to the study staff utilized in Phase I, clinicians with training in CBT and mood disorders will be added as NEW Tx therapists.

B. Participant Selection and Recruitment

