Participants ($n = 6$ for the open trial phase; $n = 60$ for the randomized phase) will be recruited from within as well as outside the MGH Bipolar Clinic and Research Program, and we plan to recruit 1 participant per month for the Phase I open trial and 2 participants per month for the Phase II randomized trial. Some subjects will be self-referred, whereas others will be referred by MGH or community clinicians. Some subjects may be obtained from media advertisements. Potential participants will not be identified through medical records, and the researchers will not contact potential participants without their permission. If a clinician feels that one of his or her patients would be potentially appropriate for this study, the patient will be encouraged to contact the PI or the research assistant directly. Alternatively, the clinician may ask the patient to give permission to be contacted over the phone by either the PI or the research assistant. Written IRB approved informed consent will be obtained from all patients before protocol-specified procedures are carried out.

Patients may be referred to the study by their treating clinicians in the MGH Bipolar Clinic and Research Program, and will be recruited according to the following criteria:

i. **Inclusion Criteria**

- Diagnosis of Bipolar Disorder (Type I or II), which is the primary focus of treatment
- Ability to give informed consent
- Currently ill (CGI-BP ≥ 3)
- Age > 18 years and < 65 years
- Overweight individuals (BMI > 25); those with BMI of 25-30 must also have high rate of percentage of body fat (greater than or equal to 32% for women and 25% for men)

ii. **Exclusion Criteria**

- Unwilling/unable to comply with study procedures
- Endorsed item, confirmed by patient's physician, on the PAR-Q
- Euthymic (CGI-BP < 3)
- Diagnosis of anorexia nervosa or bulimia nervosa in the past month
- Diagnosis of substance dependence in the past month
- Active suicidality (MADRS item 9 score > 4)
- Pregnant (as analyzed by a urine pregnancy test)
- Exercising regularly (i.e., 5 days per week for 30 min)
- Neurologic disorder or history of head trauma
- Contraindications to exercise or diet interventions (e.g., co-morbid nutritional and metabolic diseases, physical injuries)

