- iii. **Aim 3: Exploratory Aims (Phase II).** *Hypotheses 3a and 3b:* Between treatment group effects sizes (and 95% CI) will be calculated. To supplement this, Mann-Whitney tests will compare treatment groups on medical burden (as measured by FRS) (*Hypothesis 3a*) and on improvement in symptoms (MADRS, YMRS) and functioning (LIFE-RIFT) (*Hypothesis 3b*) based on change from baseline. *Hypothesis 3c.1:* We will investigate baseline BMI as a potential moderator of treatment response. The focus will be on the magnitude of the effect, not on significance testing. The between treatment group effect sizes (i.e., FRS, MADRS, YMRS, LIFE-RIFT) will be compared with those who have high baseline BMI (> 30) versus low BMI (< 30). *Hypothesis 3c.2:* Mastery of the diet (Nutrition Data System score of food diaries) and exercise (weekly exercise duration from Exercise Questionnaire) modules will mediate the association of NEW Tx and improvement in medical burden (FRS). The

dependent variable will represent change in the FRS score from time of completion of respective module. The mediators will be tested separately. Differential between treatment group effect sizes for those who did and did not master the modules will provide evidence of a mediator of treatment.

C. Rate of Attrition

Some attrition (i.e., 20%) is expected and this can result in bias and reduce power, precision and generalizability⁷⁹. Consistent with the Intent to Treat principle⁸⁰, we will continue with the assessments for the study duration, even among those who fail to comply with the treatment⁸¹. As one aspect of the feasibility study, we will assess the likelihood to attrite using the “Intent to Attend” measure⁷².

D. Power Analysis

The sample sizes for the Phase I and II trials are based primarily on the fundamental aim of this project: feasibility. The N is not based on what is needed for inferential analyses as they are not a fundamental aspect of the design. Power analyses are not indicated for the proposed exploratory analyses. We acknowledge that we will not have sufficient power to detect large effects (e.g., $d = .80$).

IX. REFERENCES

1. Hennekens C. Increasing global burden of cardiovascular disease in general populations and patients with schizophrenia. *Journal of Clinical Psychiatry*. 2007;68(suppl 4):4-7.

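### Hypothesis 3c.2 judges mediation by a mastered/not-mastered contrast that cannot be run the same way in both arms and is not a mediation estimate

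*Combined protocol and SAP*

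**What the plan says.** Section VIII.B.iii (Aim 3, Hypothesis 3c.2) proposes that mastery of the diet and exercise modules mediates the effect of NEW Tx on FRS. The exercise measure is given only as "exercise (weekly exercise duration from Exercise Questionnaire) modules". For the outcome, the "dependent variable will represent change in the FRS score from time of completion of respective module". The decision rule is "Differential between treatment group effect sizes for those who did and did not master the modules will provide evidence of a mediator of treatment".

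Other sections bear on this:

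- Section IV.A (Phase II), on the control arm: "Participants randomized to TAU who complete the first 20 weeks of the study will have the option to receive NEW Tx". TAU has no module before then.
- Section III: NEW Tx is modular, and "modules are selected based on the needs of the individual".
- Section III.B: "The goal of this module is to exercise 5 days/week, for at least 30 min each day".
- Section IV.B.ii excludes people already at that pattern: "Exercising regularly (i.e., 5 days per week for 30 min".
- Table 1 covers both arms and schedules the Exercise Questionnaire from Week 0. The footnote limiting TAU collection marks only Intent-to-Attend and Food Diaries.
- Section IV.B schedules fasting blood draws at Weeks 0, 10 and 20.

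**The concern.** The rule needs four cells: masters and non-masters in each arm, all with FRS change measured on the same clock. Mastering and completing a module are defined only for people who receive one. In TAU, one cell has no natural members and the outcome has no starting time. If the cell is filled anyway, with TAU patients who exercise for other reasons, NEW Tx patients who took up exercise with help are compared with TAU patients who exercised unaided. Randomization does not make those groups comparable.

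At stake is how this one result is read. The plan commits in advance to calling a difference between the two effect sizes evidence of a mediator. The contrast may prove incomputable, or may partly show who exercised for other reasons.

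**Working it through.** The plan gives no figure for Hypothesis 3c.2 to reproduce. Steps 1 to 3 need no assumed numbers; step 4 is an illustration.

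**1. Can the contrast be formed in both arms?**

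| Element | NEW Tx | TAU, Weeks 0 to 20 |
|---|---|---|
| Module received | Yes, selected individually (III) | No (IV.A) |
| Completion time that starts the FRS change | Exists, may differ between patients | Does not exist |
| Route to exercise mastery | Module or other exercise | Other exercise only |

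The TAU master cell is thus either empty, so that no effect among masters exists, or made up wholly of exercise that the module did not cause. The missing start time applies to the diet module too.

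**2. Would the contrast measure mediation if it could be formed?** Let T be arm, M mastery (0 or 1) and Y the FRS change.

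- Suppose the whole effect runs through mastery: Y = a + bM. Among masters the arm effect is (a + b) − (a + b) = 0. Among non-masters it is a − a = 0. The differential is 0, although mediation is complete.
- Suppose NEW Tx works only in a motivated subgroup, by a route other than exercise, and those patients are the masters in both arms. Then Y = a + cTM. The arm effect is c among masters and 0 among non-masters, so the differential is c. Arm does not change M, so nothing is mediated.

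The rule can therefore miss mediation that is present and report it where there is none. It measures an arm-by-mastery interaction.

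**3. What is left undefined?** Neither the aims (II.B) nor VIII.B.iii states a cut-off, a visit or a Week 0 reference for weekly exercise duration. Hypotheses 3a and 3b, by contrast, are explicitly based on change from baseline.

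**4. How much pre-trial exercise could count as mastery?**

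- Module goal: 5 x 30 = 150 min/week. The exclusion is the same pattern, 5 x 30 = 150.
- Below the exclusion in both days and total: 3 x 45 = 135 (135/150 = 90% of the goal) and 4 x 30 = 120 (80%). The 3 x 45 pattern appears in section I: "exercising 3 days/week for 45-min was as effective in reducing depressive symptoms as an antidepressant".
- Above 150 in total but short of five days: 4 x 45 = 180, admitted only if the exclusion is applied literally.

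Assumptions, since the documents give no figures: nobody enters at 150 min or more; a share z of 25% to 75% report 0 min at Week 0; the rest are spread evenly from 0 to 150; TAU patients do not change. At cut-off c, the TAU share that counts as masters is p = (1 − z)(150 − c)/150. Completers per arm at 20% attrition (VIII.C) are 30 x 0.8 = 24 for n = 60 (IV.A), or 20 x 0.8 = 16 for the n = 40 still given in II.

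| Cut-off | p | Expected TAU masters, 24 (16) completers | Chance of fewer than two, 24 (16) completers, binomial |
|---|---|---|---|
| 150 | 0 | 0 (0) | 100% (100%) |
| 135 | 0.025 to 0.075 | 0.6 to 1.8 (0.4 to 1.2) | 45% to 88% (66% to 94%) |
| 120 | 0.05 to 0.15 | 1.2 to 3.6 (0.8 to 2.4) | 11% to 66% (28% to 81%) |

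The cut-offs of 135 and 120 are illustrative and are not in the plan. The table shows only that, on these assumptions, the TAU master cell is empty or very small.

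**The case against.** **The rule could compare NEW Tx masters, and then non-masters, with all of TAU.** The wording may allow this, and no TAU cell would be empty. But with a common SD the TAU mean cancels: (masters − TAU)/SD − (non-masters − TAU)/SD = (masters − non-masters)/SD. What remains is a non-randomized comparison inside NEW Tx, and the FRS change still has no start time in TAU.

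**The exclusion already deals with prior exercise.** Largely so at 150 min/week, the only benchmark that the documents give for this module. The 3 x 45 dose is a background citation about depressive symptoms in a unipolar sample, not a mastery or FRS threshold. What stands is narrower: no cut-off is stated, and lower ones would let some prior exercise count.

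**A stronger reading is tempting:** that the plan chose a level of exercise over a change, and that a change score would cure the problem. The documents do not support this. The text is silent; a level is the natural reading, but it is not stated. Nor does a change score show that the module caused the exercise, because TAU patients can also increase theirs. In an illustrative simulation with people at 150 min or more at Week 0 excluded, the share of NEW Tx masters who would have qualified without the module was 1% to 20% under a level rule (at least 150 min) and 2% to 25% under a change rule (a rise of at least 60 min). All inputs were assumed: habitual mean 30 to 90 min/week, week-to-week SD 20 or 40, and a module effect drawn with mean 60 and SD 60, cut at 0.

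**Exercise from other causes is not in itself a fault in a mediator.** Correct: a mediation model uses such variation in both arms. The fault lies in sorting patients by it and comparing arms within the groups.

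**The aim is exploratory and unpowered.** True, and this sets the severity.

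**Conclusion.** The concern holds on the structure of the analysis. The contrast has no common outcome clock, its TAU master cell is empty or filled by non-module exercise, and it conditions on a post-randomization variable in a way that does not estimate mediation. This rests on the plan's text and simple algebra. The missing baseline reference, cut-off and time point is a secondary gap, limited at 150 min/week by the exclusion.

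The severity is minor. One exploratory hypothesis in a feasibility pilot is affected, and no primary aim depends on it. No size or direction of bias in the FRS effect is claimed: FRS can also move through diet and smoking, and the cell counts rest on assumed exercise distributions.

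**What to change.** In VIII.B.iii, replace the decision rule for the exercise mediator with the following:

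- **Mediator:** weekly minutes on the Exercise Questionnaire at a common visit in both arms, e.g. Week 10, kept continuous and adjusted for Week 0 minutes.
- **Models:** estimate the arm effect on exercise, and the exercise effect on FRS change with arm in the model. Report both with confidence intervals.
- **Outcome window:** one fixed window for both arms. Week 10 to 20 keeps exercise ahead of the outcome. Week 0 to 20, with exercise taken at Week 20, covers the whole treatment period but gives up temporal order.
- **Mastery split:** descriptive only.

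The cost is two or three sentences and no new visit, because the questionnaire and blood draws are already scheduled. If the Week 0 form records past exercise but not current weekly minutes, one item must be added.

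There are downsides. A Week 10 to 20 window misses earlier FRS effects, and some patients may not have finished the module by Week 10. The exercise-to-FRS step remains non-randomized. If TAU minutes barely change, the Week 0-adjusted slope rests almost wholly on the NEW Tx arm, so a gain in precision from using both arms should not be promised. The result stays exploratory and imprecise.

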Research staff will enter scale and assessments responses into the REDCap electronic assessment forms. Using 128 bit RSA Secure Socket Layer (SSL) encryption, approved users will be logged-in to machines using secured browsers behind the Partners Healthcare Systems IS corporate firewall or the RIH firewall. Staff will have a unique identifying key that will link them to the electronic study forms. This unique ID will be used in addition to a randomly generated secure password that only the staff person will have. Additional confidentiality procedures are detailed in the Human Subjects section.

B. Statistical Analyses Plan for Research Aims

Each of the statistical tests below will use a two-tailed alpha-level of 0.05.

- i. **Aim 1: Feasibility in Nonrandomized Trial (Phase I).** *Hypothesis 1a:* Descriptive statistics will be used to report the number of intervention sessions attended (we expect > 80%), number of participants recruited per month, and therapist adherence to NEW Tx (average adherence score ≥ 6). *Hypothesis 1b:* Participants will report high satisfaction (total CSQ-8 score, $M > 24^{75}$) with the treatment and acceptability (total NEW Tx Scale score, $M < 25$, or at least an average score of “agree” on half of the items).
- ii. **Aim 2: Feasibility in Randomized Trial (Phase II).** *Hypothesis 2a:* Descriptive statistics will be used to report the number of intervention sessions attended (we expect > 80%), number of participants recruited per month, randomization rate (number randomized/number consented), number of assessment sessions attended (we expect > 80%), and retention (number of study completers/number randomized) (we expect > 80%, which is conservative for diet and exercise interventions for severe mental illness^{25, 76-78}) and therapist adherence to NEW Tx (average adherence score ≥ 6). *Hypothesis 2b:* Participants will report high expectations (CEQ score) for the treatment and high satisfaction and acceptability (CSQ-8, Post-Tx Questionnaire, NEW Tx Scale).

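### Hypotheses 3a/3b: the stated analysis uses nothing from patients without a Week 20 value, and the use of early-termination values is left open

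*Combined protocol and SAP*

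**What the plan says.** Section VIII.C states: "Some attrition (i.e., 20%) is expected and this can result in bias and reduce power, precision and generalizability". It then continues: "Consistent with the Intent to Treat principle", "we will continue with the assessments for the study duration, even among those who fail to comply with the treatment". The retention target in VIII.B.ii agrees with the 20% figure.

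For Hypotheses 3a and 3b, VIII.B.iii gives two analyses: "Between treatment group effects sizes (and 95% CI) will be calculated", and, as a supplement, "Mann-Whitney tests will compare treatment groups on medical burden (as measured by FRS") and on symptoms and functioning. Both are based on change from baseline. VIII.B.iii names no visit; the 20-week horizon comes from the hypotheses in II.B.

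Other relevant provisions:
- Table 1 labels Week 20 as Post/ET, with ET defined as early termination.
- Intent to Attend (IV.C.xvi) is collected partly to judge whether attrition is ignorable.
- The opening of VIII compares dropouts with completers on baseline variables.
- VI.B.iii withdraws participants whose condition deteriorates substantially.
- IV.A.ii makes estimating an effect size a purpose of Phase II, and offers NEW Tx to TAU participants who complete the first 20 weeks.

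No analysis set, missing-data method or rule for early-termination values is given for 3a/3b.

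**The concern.** A patient with no Week 20 value has no 20-week change score, so a two-group comparison of change scores cannot use that patient's baseline or Week 10 data. The plan names attrition bias, yet nothing in the 3a/3b estimate addresses it. Intent to Attend and the baseline comparison describe who leaves. Neither enters the estimate, and a baseline comparison cannot show dropout driven by response during treatment.

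Reasons for leaving may differ by arm. Access to NEW Tx after 20 weeks gives TAU patients an incentive to stay that NEW Tx patients do not have. Withdrawal for deterioration ties some missingness to the 3b outcomes in either arm. If the mechanism or the rate differs by arm, the effect size that Phase II is meant to deliver is biased, and more patients would not remove the bias. If the shared Post/ET label led someone to treat an early value as Week 20, the estimate would mix different lengths of treatment.

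**Working it through.** The plan gives no derived figure to reproduce.

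**1. Patients affected.** The plan states Phase II as 60 (IV.A.ii) and as 40 (II). At 20% attrition, 0.20 × 60 = 12 or 0.20 × 40 = 8 patients may lack a Week 20 value, leaving 24 or 16 per arm.

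**2. Completers-only bias.** In each arm, the completers' mean change exceeds the mean in all randomised patients by (dropout fraction) × (gap), where gap = mean change in completers minus mean change in dropouts. Hence

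bias = p(NEW) × gap(NEW) − p(TAU) × gap(TAU).

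The documents do not give the gap. With 20% dropout in each arm and a gap in NEW Tx only, a gap of 0.25 to 1.0 SD gives 0.20 × 0.25 = 0.05 to 0.20 × 1.0 = 0.20 SD. Equal rates and equal gaps give 0.

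**3. Illustration by simulation.** All inputs except the 20% are assumptions:
- Outcome scored so that higher is better, SD 1 at each visit.
- Correlations 0.6 (Weeks 0 and 10), 0.7 (10 and 20) and 0.5 (0 and 20). The SD of the 20-week change is √(2 − 2 × 0.5) = 1.
- True effect 0.25 at Week 10 and 0.50 at Week 20.
- 20% overall dropout, all after Week 10, logistic in Week 10 change. The slope is the rise in log-odds of leaving per 1 SD worse change.

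| Dropout NEW Tx / TAU | Slope NEW Tx / TAU | Completers-only | Week 10 value carried as Week 20 |
|---|---|---|---|
| 20% / 20% | 1 / 1 | 0.50 | 0.45 |
| 20% / 20% | 1 / 0.5 | 0.55 | 0.44 |
| 27% / 13% | 1 / 1 | 0.57 | 0.42 |
| 20% / 20% | 1 / 0 | 0.61 | 0.42 |
| 27% / 13% | 1 / 0 | 0.64 | 0.40 |
| 20% / 20% | 1 / −1 (TAU improvers leave) | 0.71 | 0.39 |

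The formula in step 2 agrees. The simulated gap is about 0.53 SD at slope 1 and 0.29 SD at slope 0.5:
- 20%/20%, slopes 1/0: 0.20 × 0.53 = 0.11.
- 27%/13%, slopes 1/0: 0.267 × 0.53 = 0.14.
- 20%/20%, slopes 1/0.5: 0.20 × 0.53 − 0.20 × 0.29 = 0.05.

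An analysis using Weeks 0 and 10 from all randomised patients gives 0.50 in every row. That follows from the set-up, because dropout was made to depend only on observed values.

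**4. Carried values.** With equal mechanism and rates, 0.80 × 0.50 + 0.20 × 0.25 = 0.45. If the full effect were present at Week 10, 0.80 × 0.50 + 0.20 × 0.50 = 0.50, so the shortfall depends on how quickly the effect builds. Early-termination values before Week 10 were not simulated.

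**5. Bias against sampling error.** With 24 completers per arm, the standard error of the effect size near zero is √(2/24) = 0.29. A bias of 0.05 to 0.14 is 0.17 to 0.48 of that.

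**The case against.** The strongest reply is that this is a feasibility pilot. Hypotheses 3a and 3b are exploratory, VIII.D says the sample size was not set for inference, and the bias shown is about half a standard error or less in the main scenarios. That stands, and it limits the importance of the point. It does not remove it, because IV.A.ii names effect-size estimation as a purpose.

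A reader might infer that the plan contradicts its own intent-to-treat statement. The full sentence does not support that. It commits to continued assessment of non-compliers, so a NEW Tx patient who stops sessions but still attends the Week 20 visit stays in the analysis. The gap concerns patients who are no longer assessed.

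A reader might also infer that the plan prescribes a completers-only analysis, or counts early-termination values as Week 20. It states neither. Post/ET is a column label in an assessment schedule, and imputation is equally open. Nothing here rests on cell positions in Table 1, which the text extraction has shifted.

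Finally, the size depends on asymmetry between arms. The withdrawal rule for deterioration applies to both arms; only the TAU incentive to stay points clearly to a difference.

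**Conclusion.** The point holds as a gap. The plan expects attrition, says it can bias results, and states a 3a/3b analysis that uses nothing from patients without a Week 20 value and gives no rule for early-termination values.

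Under the assumptions above, completers-only gives about 0.55 to 0.64 against a true 0.50 SD, which is 10% to 28% too large (0.05/0.50 to 0.14/0.50). It reaches 0.71 if TAU improvers also leave. A Week 10 value carried as Week 20 gives about 0.40 to 0.45 in the other scenarios if half the effect is present by Week 10. These figures are illustrative. The conclusion that a completers-only comparison must overstate NEW Tx goes too far, since equal mechanism and rates give 0.50. The documents give a reason for dropout to differ by arm but no evidence of its size.

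This is a cheap improvement, worth making because the effect size is a stated product of Phase II.

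**What to change.** In VIII.B.iii:

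- **Main estimate.** For each 3a/3b outcome, report the arm difference in change from baseline to Week 20, with its 95% CI and in standardised form. Take it from a likelihood-based repeated-measures model of Weeks 0, 10 and 20 (arm by visit) including all randomised patients. The transformations already allowed in VIII can be used. Intent to Attend may serve as an auxiliary predictor at Weeks 0 and 10, where both arms have it.
- **Early-termination values.** Assign such a value to Week 10 or Week 20 only if it falls within a window of that visit stated in advance. Otherwise leave it out of the model and list it. Never count it as Week 20 by default. The window is needed because a model with three visit levels has no place for a value taken at another week.
- **Supportive.** Keep the planned effect size and Mann-Whitney test on observed Week 20 changes.
- **Sensitivity.** Shift missing NEW Tx Week 20 values by 0 to 0.5 SD in the unfavourable direction and report how the estimate moves.

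The cost is SAP wording, one extra model per outcome and one sensitivity analysis, with no added visits. The downside is reliance on approximate normality and on missingness depending only on observed data; the sensitivity analysis tests the second.
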